## **9.3. LEVEL OF SIGNIFICANCE**

The primary assessment of the dose-response will be evaluated using a 5% level of significance. Since both co-primary endpoints will be required to be significant at the 0.05 level, there is no adjustment needed for multiple comparisons.

All other reported *p*-values will be considered descriptive and hypothesis generating.

## **9.4. PROCEDURE FOR ACCOUNTING FOR MISSING, UNUSED, OR SPURIOUS DATA**

Any missing, unused, or spurious data will be noted in the final clinical study report. Multiple imputation will be employed to analyze incomplete data sets under the assumption that missing data are, at worst, characterized as missing at random (MAR). The reasons for missing data will be recorded and the impact of these reasons and any treatment group imbalance on the assumption of MAR will be evaluated. Imputation will be carried out only on the co-primary endpoints and time points.

## **9.5. PROCEDURE FOR REPORTING DEVIATIONS FROM THE STATISTICAL PLAN**

Any deviations from the statistical analysis plan will be described and a justification given in the final clinical study report.

## **10. DIRECT ACCESS TO SOURCE DATA/DOCUMENTS**

The Investigator will permit trial-related monitoring, audits, IRB review, and regulatory inspection(s) by providing direct access to source data and documents (such as tests performed as a requirement for participation in the study and other medical records required to confirm information contained in the case report form such as medical history) to the monitor.

## **11.        QUALITY CONTROL**

The progress of the study will be monitored by on-site, written, e-mail, and telephone communications between personnel at the study center and the sponsor (or designated monitor). The Investigator will allow Kala Pharmaceuticals, Inc. monitors or designee to inspect all CRFs; subject records (source documents); signed informed consent forms; HIPAA authorizations; records of investigational product receipt, storage, and disposition; and regulatory files related to the study.

## **12. ETHICS**

### **12.1. Institutional Review Board**

This protocol and the informed consent form must be approved by an appropriately constituted and qualified IRB and the approvals made available to the sponsor or designee prior to the start of enrollment into the study based on these items. Materials used to recruit subjects will be approved by the appropriate IRB and the approvals made available to the sponsor or designee prior to their use. In addition, the Investigator's Brochure should be submitted to the IRB. Written IRB approval must adequately identify the protocol and informed consent form. Copies of all approved materials, all correspondence with the IRB, and written approval from the IRB must be made available to the sponsor (or designated monitor).

Any modification of study procedures or amendments to the protocol must be approved by the IRB prior to implementation. In the event that a modification or amendment is considered by the Investigator to be immediately necessary to ensure subject safety, the Investigator will promptly notify his or her IRB and the sponsor.

Investigators will report all SAEs reported at their site to their IRB, as appropriate.

### **12.2. Informed Consent Requirements**

Written informed consent will be obtained from each participant prior to any study-related procedures being performed (prior to or upon Visit 1- Screening). A copy of the signed and dated informed consent document will be given to each subject. The original signed and dated informed consent document must be maintained in the study files at the investigative site and be available for sponsor or designee review.

Each informed consent will contain Investigator contact information with a telephone number the subject or the subject's authorized representative can call 24 hours a day if they have medical concerns.

## **13. DATA HANDLING AND RECORDKEEPING**

All procedures for the handling and analysis of data will be conducted using GCP and meet ICH guidelines and US FDA regulations for the handling and analysis of data for clinical trials.

### **13.1. Data Quality Control and Reporting**

After data have been entered into the study database, a system of computerized data validation checks will be implemented and applied to the database. Query reports pertaining to data omissions and discrepancies will be forwarded to the clinical Investigator and monitor(s) for resolution. The study database will be updated in accordance with the resolved query reports. All changes to the study database will be documented.

### **13.2. Records Retention**

The study center will retain all records related to the study in accordance with local and ICH GCP guidelines.

**14. PUBLICATION POLICY**

The institution and Investigators participating in this trial shall have no right to publish or present the results of this study without the prior written consent of the sponsor.

**16. APPENDICES**

**CONFIDENTIAL**

APPENDIX 1: SUMMARY OF EVENTS

Procedures	Visit 1	Visit 2	Visit 3	Visit 4	Visit 5	Visit 6
	Screening	Randomization	[REDACTED]	Study Visit	[REDACTED]	End of Study Visit
	14 ± 1 Days Prior to Day 1	Day 1	Day 8 (±1 day)	Day 15 (±1 day)	Day 22 (±1 day)	Day 29 (±1 day)
Informed Consent, HIPAA Authorization and Medical History	X					
Concomitant medication query	X	X	X	X	X	X
UPT a	X					X
Inclusion/Exclusion	X	X				
AE Assessment	X	X	X	X	X	X
Subject-rated assessment of ocular discomfort	X	X	X	X	X	X
[REDACTED]	X	X c	X c	X c	X c	X c
Investigator-rated assessment of bulbar conjunctival hyperemia	X	X		X		X
[REDACTED]		X		X		X
BCVA	X	X		X		X
Slit lamp biomicroscopy	X	X		X		X
Corneal fluorescein staining	X	X		X		X
Lissamine Green conjunctival staining	X	X		X		X
Unanesthetized Schirmer Test Assessment	X					
IOP measurement	X	X		X		X
Dilated ophthalmoscopy	X					X

Procedures	Visit 1	Visit 2	Visit 3	Visit 4	Visit 5	Visit 6
Investigational product administration in-clinic	X b	X				
Dispense investigational product	X b	X		X		
	X b	X	X	X	X	
Collect investigational product		X b				X
		X b	X	X	X	X

aWomen of childbearing potential only; bRun-In Product [REDACTED]

## APPENDIX 2: SUBJECT-RATED OCULAR DISCOMFORT ASSESSMENT

Subjects will be asked to subjectively rate their ocular discomfort severity and frequency at Visits 1-6. Investigator site designees will ask the subject the following question and record their answer in the eCRF. This assessment is a general assessment of both eyes. There will not be a question for each individual eye.

### Severity of Symptoms

On average over the past day, how would you rate the severity of your ocular discomfort associated with dry eye (for example, dryness or irritation)?

0 = None

1 = Mild

2 = Moderate

3 = Severe

4 = Very Severe

### Frequency of Symptoms

On average over the past day, how often have you had this level of ocular discomfort associated with dry eye (for example, dryness or irritation)?

0 = Never

1 = Sometimes

2 = Often

3 = Constantly

**APPENDIX 3: [REDACTED] ASSESSMENT**

Subjects will be asked to subjectively rate their ocular discomfort severity and frequency at Visit 1 for eligibility. [REDACTED]

[REDACTED] The total length of the line from [REDACTED] is 100 mm. The length of the line between the [REDACTED] starting point and the first point where the subject's mark crosses the line will be measured and recorded in millimeters. This assessment is a general assessment of both eyes. There will not be a question for each individual eye.

**[REDACTED] SEVERITY ASSESSMENT**

Please place a single line across the line below to indicate how severe, [REDACTED] you feel your eye discomfort (for example, dryness or irritation) was:

[figure not shown]
[REDACTED] \_\_\_\_\_ [REDACTED]

**[REDACTED] FREQUENCY ASSESSMENT**

Please place a single line across the line below to indicate how often, [REDACTED] you feel your eye discomfort (for example, dryness or irritation) was:

[REDACTED] \_\_\_\_\_ [REDACTED]

**APPENDIX 4: INVESTIGATOR-RATED ASSESSMENT OF BULBAR CONJUNCTIVAL HYPEREMIA**  
Investigators will rate bulbar conjunctival hyperemia at Visits 1, 2, 4, and 6 using the CCLRU Grading Scale.

- (0) None
- (1) Very Slight
- (2) Slight
- (3) Moderate
- (4) Severe

## APPENDIX 5: UNANESTHETIZED SCHIRMER TEST EVALUATION

Unanesthetized Schirmer Test evaluation will be conducted at Visit 1. Identical Schirmer Test strips will be supplied to each site. When conducting assessments room temperature and humidity should be relatively consistent throughout each visit and throughout the study. Please make certain to allow at least 20 minutes between any corneal staining evaluations and the unanesthetized Schirmer Test.

### Unanesthetized Schirmer Test

- While still in the plastic sheath, fold the notched end of the unanesthetized Schirmer Test strip at the apex of “v”. Additionally, fold a partial second fold at the halfway point of the strip so that the strip does not lie directly in the subject’s line of sight.
- Remove the right eye strip from the sheath.
- Ask the subject to look up and gently draw the right lower lid in a downward and temporal direction.
- Place the rounded end of the strip toward the temporal one-third of the lower eyelid.
- Repeat this procedure in the left eye.
- Darken the room, but ensure that the Large E or the ETDRS chart is visible.
- Instruct the subject to relax and look at the chart while blinking normally or have subject gently close eyes.
- Strips are removed after 5 minutes.
- After removing the strips, with a sharp pencil draw a horizontal line across the leading edge of moisture and a second horizontal line across the lowest point of moisture.
- Using a ruler and/or the millimeters recorded on the strips, measure a point halfway between the 2 lines and record this as the amount of wetting.
- Retain Schirmer strips in source documentation.

## APPENDIX 6: BEST-CORRECTED VISUAL ACUITY

BCVA will be conducted at Visits 1, 2, 4 and 6.

Visual acuity testing should precede any examination requiring contact with the eye or instillation of study dyes. LogMAR visual acuity must be assessed using an ETDRS or modified ETDRS chart. Visual acuity testing should be performed with best correction using subject's own corrective lenses (spectacles only) or pinhole refraction.

An ETDRS or modified ETDRS chart may be used. If a Lighthouse chart is used (24.5" by 25"; either reflectance or retro-illuminated), the subject must view the chart from a distance of exactly 4 meters (13.1 feet). If smaller reproductions (18" by 18", e.g., Prevent Blindness) are used, the subject viewing distance should be exactly 10 feet. Reflectance wall charts should be frontally illuminated (60 watt bulb or a well-lit room).

The subject should be positioned according to the elevation of the chart (either seated or standing) so that the chart is at a comfortable viewing angle. The right eye should be tested first. The subject should attempt to read each letter, line-by-line, left to right, beginning with line 1 at the top of the chart. The subject should be told that the chart has letters only, no numbers. If the subject reads a number, he or she should be reminded that the chart contains no numbers, and the examiner should then request a letter instead of the number. The subject should be asked to read slowly, about 1 letter per second, to achieve the best identification of each letter. He/she is not to proceed to the next letter until he/she has given a definite response. If the subject changes a response before he has read aloud the next letter, then the change must be accepted.

Maximum effort should be made to identify each letter on the chart encouraging the subject to guess. When it becomes evident that no further meaningful readings can be made, the examiner should stop the test. The number of letters missed or read incorrectly should be noted.

**In order to provide standardized and well-controlled assessments of visual acuity during the study, consistently use the same lighting conditions during the entire study.**

*Calculations:* logMAR VA = Baseline value + (n X 0.02)

where: the baseline value is the logMAR number of the last line read (at least 1 letter

read correctly in this line), and

“n” is the total number of letters missed up to and including the last line read,  
and

“0.02” is the value for each letter

## APPENDIX 7: SLIT LAMP BIOMICROSCOPY

The biomicroscopy exam will be performed at Visits 1, 2, 4 and 6. It should be performed with the slit lamp using a beam of width and intensity to provide optimal evaluation of anterior segment.

This procedure will be performed in the same manner for all subjects observed at the Investigator's site.

### Lashes

0 = Normal

1 = Abnormal

### Eyelid

#### Eyelid Margin Hyperemia (lower eyelid):

0 = Normal	Normal age-appropriate redness and vasculature.
1 = Mild	Slightly dilated blood vessels; vessels colored pink; present in greater than 25% of the lower eyelid margin
2 = Moderate	More apparent dilation of blood vessels; vessel color red, present in greater than 25% of the lower eyelid margin.
3 = Severe	Increased vascularity of the eyelid margin, numerous and obvious dilated blood vessels, deep red in color, present in greater than 25% of the lower eyelid margin.
4 = Very Severe	Clearly increased vascularity of the eyelid margin; numerous dilated blood vessels deep red color, present in greater than 75% of the lower eyelid margin.

#### Character of Meibomian Gland Content (middle part of lower lid, n = 10)

0 = Normal Clear liquid

1 = Mild Hazy, turbid liquid

2 = Moderate Turbid liquid with clumps

3 = Severe Solid (paste)

**The most severe finding in any one meibomian gland should be recorded for this evaluation**

#### Expressibility of Meibomian Gland (middle part of lower lid, n = 10)

0 = Normal 9 – 10 glands expressible

1 = Mild 6 – 8 glands expressible

2 = Moderate 3 – 5 glands expressible

3 = Severe 1 – 2 glands expressible

**Edema**

- 0 = Normal, no swelling of the lid tissue  
1 = Abnormal

**Conjunctiva**

**Edema**

- 0 = Normal, no swelling of the conjunctiva  
1 = Abnormal

**Cornea**

**Infiltrates**

- 0 = Absent  
1 = Present

**Endothelial Changes**

- 0 = Normal, None  
1 = Abnormal, pigment, keratoprecipitates, guttata

**Edema**

- 0 = Normal None, transparent and clear  
1 = Abnormal

**Anterior Chamber**

**Cells**

- 0 = Normal, No cells seen  
1 = Abnormal (+ to +++ cells)

**Flare**

- 0 = Normal, No Tyndall effect  
1 = Abnormal, Tyndall beam in the anterior chamber

**Lens Pathology**

- 0 = Normal; no opacity in the lens  
1 = Abnormal; existing opacity in the lens; aphakic or pseudophakic eyes or other abnormal findings.

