**8.3. PROCEDURES FOR AE REPORTING BY THE INVESTIGATOR**

AEs will be monitored throughout the study and will be recorded on the CRF with the date and time of onset, date and time of resolution, severity, seriousness, causality (relationship to use of investigational product), treatment required, and the outcome.

To elicit AEs, simple questions with minimal suggestions or implications should be used as the initial questions at all evaluation points during the trial. For example:

- How have you felt since your last assessment?
- Have you had any health problems since your last assessment?

The severity of each AE should be categorized as mild, moderate, or severe.

The causality of use of investigational product in relation to the AE will be assessed by the Principal Investigator after careful medical consideration and categorized as unrelated, unlikely, possible, probable, or definite.

If an AE occurs, the Investigator will institute support and/or treat as deemed appropriate. If a non-SAE is unresolved at the time of the last day of the study, an effort will be made to follow up until the AE is resolved or stabilized, the subject is lost to follow-up, or there is some other resolution of the event. The Investigator should make every attempt to follow SAEs to resolution.

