#### 9.1.3. Analysis of Safety

Analysis of safety data will be presented for all subjects in the Safety population (i.e., all subjects receiving randomized investigational product). AEs will be coded using Medical Dictionary for Regulatory Activities (MedDRA, most current version) and categorized by system organ class using preferred terms. AEs will be tabulated by study group with respect to their Severity and relationship to the investigational product. Ophthalmoscopy findings will be summarized descriptively. IOP measurements, BCVA and Biomicroscopy will be summarized as safety outcomes.

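### Ten of the 13 slit-lamp items have only two codes, so an eye already coded 1 on an item at baseline cannot register worsening on that item; gland expressibility has no code for zero

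*Combined protocol and SAP*

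**What the plan says.** Sections 3.4 and 8.1 list slit-lamp biomicroscopy as a safety endpoint and parameter. Appendix 7 schedules it at Visits 1, 2, 4 and 6 and defines the items and codes.

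- **Lens pathology.** Code 0 is a lens without opacity. Everything else is "1 = Abnormal; existing opacity in the lens; aphakic or pseudophakic eyes or other abnormal findings".
- **Endothelial changes.** Code 0 is normal. The only other code is "1 = Abnormal, pigment, keratoprecipitates, guttata".
- **Scleral injection.** Code 0 requires no redness at all; anything else is 1.
- **Meibomian gland expressibility.** Ten glands are examined, and the worst code is "3 = Severe 1 – 2 glands expressible".

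On analysis, Section 9.1.3 says only that "IOP measurements, BCVA and Biomicroscopy will be summarized as safety outcomes". It gives no shift table and no definition of worsening.

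On eligibility (Section 4.1.2), exclusion 11 bars penetrating intraocular surgery only if it was within 3 months before Visit 1 or is anticipated. Exclusion 13 bars only congenital absence of the glands. Neither lens opacity nor guttata is named. Inclusion criterion 5b (Section 4.1.1) requires a level of bulbar conjunctival hyperemia at Visits 1 and 2; the threshold is redacted.

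**The concern.** A safety examination repeated after dosing should be able to show change from the pre-dose state. A two-code item does this for an eye that starts at 0. For an eye that starts at 1 it cannot show worsening. Two of the items put long-standing findings into code 1, so some subjects can be expected to start there.

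The endothelial item is the clearest case, because the loss is not only one of degree: a different finding can appear and leave the code unchanged. The study compares a corticosteroid with vehicle, so a reader of the biomicroscopy summary will want to know whether an unchanged score means that nothing happened or that nothing further could be recorded. The codes alone cannot separate the two. A more detailed table written later cannot recover a distinction that was never captured.

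**Working it through.** The plan states no figure on this point, so there is none to reproduce. The check is a count of codes, a comparison with the eligibility criteria, and one illustration under a stated assumption.

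**1. Count of items in Appendix 7**

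| Type | Items | Number |
|---|---|---|
| Graded | lid margin hyperemia (0–4), gland content (0–3), gland expressibility (0–3) | 3 |
| Two codes (0/1) | lashes, lid edema, conjunctival edema, corneal infiltrates, endothelial changes, corneal edema, anterior chamber cells, flare, lens pathology, scleral injection | 10 |
| Total | | 13 |

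**2. The ceiling**

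Largest recordable worsening = highest code − baseline code. For a two-code item it is 1 − 0 = 1 from baseline 0, and 1 − 1 = 0 from baseline 1.

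**3. Items where baseline 1 is plausible**

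| Item | What gives code 1 at entry | Can such an eye enter? | What is lost |
|---|---|---|---|
| Lens | any opacity, aphakia, pseudophakia | Yes; only recent or anticipated surgery is barred | progression of an existing opacity |
| Endothelium | guttata or pigment | Yes; not named as exclusions | new keratoprecipitates (1 to 1) |
| Scleral injection | any redness | Possibly; conjunctival hyperemia is required for entry, but the documents do not say how the two scores relate | increase in redness on this item |

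For infiltrates, corneal edema, cells and flare, the documents give no reason to expect code 1 at entry. A new event there moves 0 to 1 and is captured. Cells graded + to +++ share one code, so a new event is seen but its degree is not.

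**4. Gland scales**

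The expressibility codes cover 9–10, 6–8, 3–5 and 1–2 glands, that is 2 + 3 + 3 + 2 = 10 of the 11 possible counts from 0 to 10. The uncovered count is 0. In an eye where nothing can be expressed, the gland-content item has nothing to grade and no code for that state.

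**5. Illustration only**

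The documents give no proportion of eyes coded 1 at entry. Assume a fraction b between 0% and 60% on one item, about 75 subjects per arm (150 randomized approximately 1:1), and one eye per subject. The eyes per arm that can still worsen number n = 75 × (1 − b). If no worsening is seen among them, the one-sided 95% upper bound on the worsening rate in those eyes is 1 − 0.05^(1/n).

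| b (assumed) | n | Upper bound |
|---|---|---|
| 0% | 75 | 3.9% |
| 20% | 60 | 4.9% |
| 40% | 45 | 6.4% |
| 60% | 30 | 9.5% |

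The bound says nothing about the eyes already coded 1.

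**The case against.** Normal/abnormal coding is a common-sense choice for a 28-day Phase 2 study, and several stronger readings do not survive.

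- **The eye as a whole cannot show worsening.** A reader might infer this, but the ceiling applies item by item. The same eye can change on the other items, three of them graded, and on other scheduled examinations: hyperemia (0–4), corneal staining (0–15), BCVA and IOP at Visits 1, 2, 4 and 6.
- **Adverse event reporting would miss examination findings.** Section 8.3 does say "To elicit AEs, simple questions with minimal suggestions or implications should be used", but it describes these as the opening questions. Section 8.2 defines an adverse event without requiring symptoms, and Appendix 1 schedules AE assessment at all six visits. New precipitates could be reported. What stands is narrower: no section requires a slit-lamp change to be recorded as an adverse event.
- **All ten items are affected.** The named chronic findings sit in two items, lens and endothelium. Scleral injection is only a possibility. Exclusion 17f also lets the investigator keep out severe ocular conditions that could confound assessments.
- **Observed worsening shrinks by a factor of 1 − b.** With b from 20% to 60% this would be 0.8 down to 0.4. It rests on an assumed prevalence and on equal worsening rates in eyes coded 0 and 1. The second assumption is doubtful for the lens: a pseudophakic eye has no natural lens left to opacify. Randomization should also make b similar in the two arms, so the ratio between arms would be largely preserved while absolute differences shrink.
- **The report will show no change where change was hidden.** No such table is specified. Section 9.1.2 defers detail to a Statistical Analysis Plan, and neither its table shells nor the eCRF is in the text available here. Comment fields for abnormal findings cannot be ruled out.

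The code definitions, the eligibility of these eyes and the missing zero-gland code all stand.

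**Conclusion.** The point holds as a minor, inexpensive improvement to safety data capture. As Appendix 7 is written, an eye coded 1 on any of ten items at Visit 2 cannot register worsening on that item. The practical weight falls on lens pathology and endothelial changes, and possibly on scleral injection.

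The consequence is lost sensitivity in the biomicroscopy summary. The documents do not support a claim of quantified bias between arms. The size cannot be computed, because neither the proportion coded 1 at entry nor any worsening rate is given; the range in the working shows only how the information would thin out under assumed proportions. The co-primary endpoints and the sample size are not touched.

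The missing code for zero expressible glands is a separate gap in the scale. It stands on the text alone and needs no assumption.

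**What to change.** 1. In Appendix 7 and the eCRF, add one field per item and eye at Visits 4 and 6: *new or worse than Visit 2, yes/no*. This lifts the ceiling on all ten two-code items without regrading any of them.
2. Record keratoprecipitates separately from pigment and guttata.
3. Define expressibility code 3 as 0 to 2 glands, and add *not assessable* to gland content for eyes in which nothing can be expressed. Recoding expressibility alone would leave the content item unscorable in those eyes.
4. In Section 9.1.3, tabulate by arm the number of subjects with any new or worse finding, alongside the score summary.

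The cost is a few more eCRF fields, one more safety table and revised wording in Appendix 7. The examination, the visits and the staffing stay as they are. The change has to be made before data collection, because a judgement of change cannot be rebuilt afterwards from the 0/1 codes.
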